 12. Cardiovascular biomarker : Glucose et al will be included in the summary of clinical chemistry, so there will be no separate summary for CV biomarkers
 13. Renal biomarkers: Urine Retinol Binding Protein, Retinol Binding Protein Cystatin C. CKD-EP1 GFR using Cystatin C (derived in Section 13.6.3) will also be summarized
 14. Repeat for CAB/RPV, CAB, RPV respectively.
 15. Separate listings for exposure to abacavir, history of drug allergies, family conditions, skin rash, symptoms, vital signs, individual symptoms and diagnostic category assignment.
 16. Separate listings for time of event: RUCAM score, biopsy, imaging, past/ current conditions and follow up
 17. One summary of subjects and another table showing Subject Ids.
 18. No lists are planned for eCSSR data.
 19. Patient profiles are not planned. But it can be produced in adhoc way, as necessary.
 20. Event-level summary: Percentages based on total number of ISR events within each treatment group including distribution of grade, duration, and event characteristics;

21. Subject-Level summary of characteristics of ISR AE (Overall and by Common ISRs); Percentage based on number of subjects within each treatment group; Includes distribution of grade and max grade, event characteristics, number of events per subject, rate of number of events per injection visit;
22. A corresponding plot of all grades and a separate plot of grade 3-5 events will be produced
23. Needle Length will be categorized into: <2 and ≥ 2 inch (please refer to Section 5.4 for the additional subgroup of ISR).
24. Please refer to Section 13.6.3 for defining percentage change from Baseline in Lipids

For the summary of Injection Site Reaction Adverse Events by Visit and Maximum Severity (Overall and by Common ISRs): ISRs will be assigned based on onset date to the most recent planned IM injection visit prior or equal to the AE onset date.

Maximum grade at each visit will be derived as the maximum grade among ISRs assigned to the particular visit, with consideration for whether the summary applies to a particular preferred term (vs. across preferred terms), drug-related associated to CAB and/or RPV, or stratification by subgroup (such as needle length).

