	Q4W IM Arm: For subjects continuing into Extension Phase: Maintenance Treatment Start Date < Date ≤ Date of Nominal Week 52 visit For subjects not continuing into Extension Phase: Maintenance Treatment Start Date < Date ≤ LTFU ART Start Date
Extension	Subjects Switching from Maintenance Current ART Arm to Q4W IM: Start Date of Extension Phase Oral lead-in of CAB + RPV < Date ≤ LTFU ART Start Date Subjects continuing maintenance Q4W IM into Extension phase Date of Nominal Week 52 Injection < Date ≤ LTFU ART Start Date

- Date = start or assessment date
- Maintenance Treatment Start Date: refer to Treatment Start Date in Section 13.6.1

Table 18 Assignment of Study Phases for Concomitant medication/ART

Concomitant during:	Date range
Maintenance	Current ART Arm: Maintenance Treatment Start Date ≤ Medication Taken < Start Date of Extension Phase Oral CAB + RPV (expected to be Nominal Week 52) or Withdrawn date prior to Extension Phase
	Q4W IM Arms: For subjects not continuing into Extension Phase: Maintenance Treatment Start Date ≤ Medication Taken < LTFU ART Start Date For subjects continuing into Extension Phase: Maintenance Treatment Start Date ≤ Medication Taken < Date of Nominal Week 52 visit
Extension	Date of nominal Week 52 visit ≤ Medication Taken < LTFU ART Start Date

Note: ART stopped on or before the Maintenance Treatment start date will not be assigned to the Maintenance Phase; ART stopped on or before the date of nominal Week 52 visit will not be assigned to Extension phase.

If a partial date for medication/ART is recorded in the eCRF, the following convention will be used to assign the medication:

- if the partial date is a start date, a '01' will be used for missing days and 'Jan' will be used for missing months;
- if the partial date is a stop date, a '28/29/30/31' will be used for the missing day (dependent on the month and year) and 'Dec' will be used for the missing month; for medications recorded separately in the eCRF as prior ART, the earlier of this imputed date or the day before IP start will be used.

The recorded partial date will be displayed in listings.

Table 19 Assignment to Long-Term Follow-Up Phase

Study Phase	Date range
Long-Term Follow-Up	Date > max(Last IM Injection Date, Last Oral Bridging End Date)

- Date = Assessment/Start Date

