13.4.2.1. Treatment States for AE Data

For adverse events, partial AE start date will use imputation as described in Section 13.7.2.1. In the case of a completely missing start date, the event will be considered to have started On-treatment at Maintenance phase unless an end date for the AE is provided which is before start of study treatment at Maintenance phase; in such a case the AE is assigned as Pre-treatment.

Within each treatment study phase, only those AE with onset date within the ranges shown in Table 20 will be considered 'on-treatment' for the given phase. The onset date will be derived Based on Table 18.

Table 21 AE onset date, AE duration and relation to study treatment

	Definition
Onset date/study day Since 1 st Dose of each study phase (Days)	If Treatment Start Date > AE Onset Date = AE Onset Date - Treatment Start Date If Treatment Start Date ≤ AE Onset Date = AE Onset Date - Treatment Start Date + 1 Missing otherwise.
Duration (Days)	AE Resolution Date – AE Onset Date + 1
Drug-related	If relationship is marked 'YES' on Inform/CRF OR value is missing.

NOTES:

- Onset date/study day will be derived for each study phase, respectively (refer to Section [13.6.1](#))

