
The Study Day of an event (e.g., lab assessment, vital sign, ECG, start date of AE or HIV associated condition) will be derived as the number of days between the date of the event and the start date of study treatment on Maintenance phase as follows:
 
if date of event \geq start date of study treatment, then
 
 • Study Day = date of event - start date of treatment on Maintenance phase + 1 
if date of event < start date of study treatment, then
 
 • Study Day = date of event - start date of treatment on Maintenance phase 
Note that the start date of study treatment on Maintenance phase is considered to be on Study Day 1 and the day before this is Study Day -1; i.e., there is no Study Day 0.

Extension Phase Study Day

The Extension Phase Study Day of an event (e.g., lab assessment, vital sign, ECG, start date of AE or HIV associated condition) will be derived as the number of days between the date of the event and the initial start date of Extension phase IP as follows:
 
if date of event \geq start date of extension phase IP, then
 $\text{Extension Phase Study Day} = \text{date of event} - \text{start date of Extension phase IP} + 1$ 
if date of event < start date of Extension Phase IP, then
 $\text{Extension Phase Study Day} = \text{date of event} - \text{start date of Extension phase IP}$ 
Note that the start date of Extension phase IP is considered to be on Extension Phase Study Day 1 and the day before this is Extension Phase Study Day -1; i.e., there is no Extension Phase Study Day 0.

Long-Term Follow Up Study Day
The Long-Term Follow Up (LTFU) Study Day of an event (e.g., lab assessment, start date of AE or HIV associated condition) will be derived as the number of days between the date of the event and the end of IP treatment [i.e. $\max(\text{Last IM Injection Date}, \text{Last Oral Bridging End Date})$] as follows: If the onset of event falls in Long-term Follow up phase, then 
 • LTFU Study Day = date of event - end date of IP
Post-baseline

 • Post-baseline refers to the combined time phases of On-treatment and Post-treatment. Post-baseline may be further specified according to phase(s) of the study: Maintenance and Extension (for example, post-baseline across the maintenance and extension phases combined).
Study treatment/drugs

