13.7.2.1. Handling of Missing and Partial Dates

Element	Reporting Detail
General	
 Partial dates will be displayed as captured in subject listing displays.
Adverse Events	
 The eCRF allows for the possibility of partial dates (i.e., only month and year) to be recorded for AE start date; that is, the day of the month may be missing. In such a case, the following conventions will be applied for calculating the time to onset and the duration of the event: 
 Missing Start Day: First of the month will be used unless this is before the start date of study treatment; in this case the study treatment start date will be used and hence the event is considered On-treatment as per Appendix 4: Study Phases and Treatment State Missing Stop Day: Last day of the month will be used, unless this is after the stop date of study treatment; in this case the study treatment stop date will be used. Completely missing start or end dates will remain missing, with no imputation applied. Consequently, time to onset and duration of such events will be missing.
Concomitant Medications/ Medical History	
 Partial dates for any concomitant medications recorded in the CRF will be imputed using the following convention: 
 If the partial date is a start date, a '01' will be used for the day and 'Jan' will be used for the month If the partial date is a stop date, a '28/29/30/31' will be used for the day (dependent on the month and year) and 'Dec' will be used for the month. For medications recorded in the eCRF as prior ART, the earlier of this imputed date or the day before Screening date will be used. The recorded partial date will be displayed in listings.
Health outcomes	
 For the health outcomes questionnaire data, please refer to Section 13.6.6. For the summary of individual item scores outputs, missing scores will not be computed.

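### The imputation rule for a missing AE stop day caps the date at treatment stop with no floor at onset, so an AE starting after that date gets a duration of zero or less

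*SAP*

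**What the plan says.** SAP 13.7.2.1 (Adverse Events row) introduces its partial-date rules by saying that "the following conventions will be applied for calculating the time to onset and the duration of the event". When the day of resolution is not recorded, the default and its exception read: "Last day of the month will be used, unless this is after the stop date of study treatment". Where the exception applies, the replacement value is given by the words "in this case the study treatment stop date will be used". Nothing in the rule stops the imputed date from falling before onset or before the recorded month.

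Table 21 in 13.4.2.1 defines duration as "AE Resolution Date – AE Onset Date + 1".

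The SAP does not define the treatment stop date for this rule. Two candidates appear elsewhere:

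- Long-Term Follow Up Study Day in 13.6.1 is the "number of days between the date of the event and the end of IP treatment", written as "LTFU Study Day = date of event - end date of IP". The anchor is the later of the last injection and the end of oral bridging. Table 19 starts long-term follow-up from the same point: "max(Last IM Injection Date, Last Oral Bridging End Date").
- Table 20 (on-treatment state) and the overall exposure formula in 13.6.2 run to 35 days after the last injection.

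Duration is reported. Note 20 to Table 5 describes the event-level injection-site-reaction (ISR) summary as "including distribution of grade, duration, and event characteristics". This is Table 3.40, a headline deliverable. Tables 3.41 and 3.42 repeat it for later phases, and Figures 3.5 to 3.7 plot ISR onset and duration.

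**The concern.** A date on which dosing ended says nothing about when an adverse event resolved. It is a poor cap for any AE, and a particularly poor one for a long-acting injection, where a reaction follows the dose. If treatment stop means the last injection, every reaction to that injection starts on or after the cap date. Under Table 16, AEs in a Q4W participant who does not enter the Extension Phase stay in the Maintenance Phase until the day before follow-up ART starts, so these reactions belong in the Maintenance Phase ISR displays.

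The error also runs one way. The cap needs a treatment stop date, and Note 2 to Table 20 applies last-dose dates only to permanent discontinuers. Participants still on treatment keep month-end, while those who stopped can only have durations shortened. Section 13.6.4 lists intolerability of injections among treatment-related reasons for discontinuation, so some of the shortened reactions could be ones that led to stopping. At stake are zero or negative values, or silently shortened ones, in the ISR duration summaries.

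**Working it through.** The SAP states no figure on this point, so there is none to reproduce. The check is date arithmetic.

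**Inputs.** S = treatment stop date. Imputed stop = last day of the resolution month, replaced by S if that day is after S (13.7.2.1). Duration = imputed stop − onset + 1 (Table 21).

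**General result.** Let onset = S + k with k ≥ 1. The event resolves on or after onset, so the end of its resolution month is after S and the cap always applies. Duration = S − (S + k) + 1 = 1 − k, whatever the true duration. For k = 0, duration is 1 day if month-end is after S. If S is itself the last day of the resolution month, the uncapped result is also 1 day.

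**Two readings of S.** The rule was run for every last-injection date in a 365-day year, true durations of 1 to 30 days, and selected onsets from 0 to 60 days after the last injection:

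| Onset, days after last injection | S = last injection (no bridging) | S = last injection + 35 |
|---|---|---|
| 0 | 1 | 1 to 36 |
| 1 | 0 | 1 to 35 |
| 3 | −2 | 1 to 33 |
| 7 | −6 | 1 to 29 |
| 28 | −27 | 1 to 8 |
| 35 | −34 | 1 |
| 36 | −35 | 0 |
| 60 | −59 | −24 |

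Under the first reading every tested case with onset at least one day after the last injection gives zero or less. Under the second this happens only from day 36.

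**Worked dates, S = last injection on 12 June.** In each case the stop is recorded only as June.

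- Onset 12 June: 12 − 12 + 1 = 1 day.
- Onset 13 June: 12 − 13 + 1 = 0 days.
- Onset 15 June: 12 − 15 + 1 = −2 days. Uncapped month-end gives 30 − 15 + 1 = 16 days.

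**Wrong month.** Last injection 27 June, onset 28 June, stop recorded as July. The imputed stop is 27 June, the month before the one the site entered, and the duration is 0.

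**Same injection on 12 June, S = last injection + 35 = 17 July.**

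- The 15 June reaction keeps 16 days, because 30 June is before 17 July.
- Onset 10 July (day 28), stop recorded as July: 17 − 10 + 1 = 8 days, against 31 − 10 + 1 = 22 uncapped. Shortened but possible.
- Onset 18 July (day 36), stop recorded as July: 17 − 18 + 1 = 0 days.

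**Without the cap.** Month-end alone gives durations of 1 to 60 days across the onsets rerun without the cap (0, 1, 3, 7 and 28 days), with no non-positive value.

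**The case against.** The strongest objection is that the ISR consequence depends on an undefined term. The end-of-IP anchor in 13.6.1 was written for counting follow-up days. The start-day rule in the same row of 13.7.2.1 refers to on-treatment status under Appendix 4, where the window extends 35 days past the last injection. On that reading, reactions starting on days 0 to 35 keep positive durations. This stands. A reader might infer that every reaction to the last injection gets a duration of zero or less, but the SAP does not support that. It fails under the +35 reading. Even under the last-injection reading, same-day onsets get 1 day, and where oral bridging follows the last injection the cap moves to the end of bridging.

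Second, the trigger may be rare. The lead-in mentions partial dates only for AE start, and completely missing end dates stay missing and give no duration. This also stands as a limit on size, but the section still writes an explicit stop-day rule, and that rule is what would be programmed.

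Third, a reader might point to large negative values in long-term follow-up, such as −98 days for an onset on 12 June after a last injection on 5 March (99 days later, 1 − 99). The arithmetic is right, but such a value reaches no listed duration display: the follow-up AE tables (3.12 and 3.24) are by system organ class, with maximum toxicity or seriousness, not duration.

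Finally, listings show partial dates as captured, so the recorded month stays visible. That helps a reader of listings but does not correct the tables or figures.

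**Conclusion.** The rule is wrong as written, with minor consequences. Under either reading of treatment stop, an AE starting k ≥ 1 days after that date gets 1 − k days, and the imputed resolution can fall in an earlier month than the one recorded. How far this reaches reactions to the last injection depends on the reading: onsets from the day after the last injection (with no later oral bridging), or only onsets from day 36. In both cases other durations can be shortened without looking impossible. The same fault applies in the Current ART arm to AEs starting after ART is stopped.

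The conclusion assumes that the rule is programmed literally and that some AEs have a known stop month, a missing stop day and a treatment stop date. The SAP gives no count, and it may be small. A reader might infer a material bias in the ISR results from the one-sided direction of the error; the direction follows from the rule, but nothing in the SAP lets its size be estimated. AE incidence and the efficacy endpoints do not use the imputed stop date and are unaffected.

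**What to change.** Replace the stop-day rule in 13.7.2.1 with: for a missing AE stop day, use the last day of the recorded month, limited only by date of death, last contact or data cut-off, and never earlier than the onset date. Remove the treatment-stop cap. The rule then no longer needs a definition of treatment stop date for the injectable arm, so the ambiguity goes with it. It would also match the partial stop-date convention for concomitant medications in the same section, which uses month-end with no treatment-stop cap.

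The cost is one sentence in the SAP and about one line of code. The only side effect is some longer reported durations, since month-end is the latest day consistent with the recorded month; that already applies to participants still on treatment.

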3.31.	Safety	AE1	Summary of Adverse Events Leading to Withdrawal/Permanent Discontinuation of Investigational Product by System Organ Class– Maintenance Phase	CS Core	HL, WK48
3.32.	Safety	AE1	Summary of Adverse Events Leading to Withdrawal/Permanent Discontinuation of Investigational Product by SOC – Maintenance + Extension Phase	CS Core(for Q4W arm only)	WK48, 96, EOS
3.33.	ESP	AE1	Summary of Adverse Events Leading to Withdrawal/Permanent Discontinuation of Investigational Product by SOC – Extension Phase	CS Core(for Current ART arm only)	WK48, 96, EOS

Safety Tables (Displays will be for both treatment arms, unless specified)					
No.	Population	IDSL / TST ID / Example Shell	Title	Programming Notes	Deliverable [Priority]
3.34.	Safety	AE1	Summary of Adverse Events Leading to Withdrawal/Permanent Discontinuation of Investigational Product by SOC – Oral Lead-in Period at Maintenance Phase	CS Core(for Q4W arm only)	WK48
3.35.	Safety	AE1	Summary of Common (>=5%) Non-Serious Adverse Events – Maintenance Phase	CS Core	WK48
3.36.	Safety	EudraCT Non-serious AE AE15	Summary of Subjects and Number of Occurrences of Common (>=5%) Non-Serious Adverse Events by System Organ Class – Maintenance Phase	CS Core for FDAAA and EMA disclosure requirements. EudraCT Use macro TD_AE4VCTR for New Data Disclosure HARP Reporting Tools	WK48
3.37.	Safety	EudraCT SAE AE16	Summary of Subjects and Number of occurrences of SAEs, Drug-related AEs, Fatal SAEs, and Drug-related SAEs – Maintenance Phase	CS Core for FDAAA and EMA disclosure requirements. EudraCT	WK48
3.38.	Safety	Shell TS2.1	Summary of Cumulative Adverse Events by Visit– Maintenance Phase	Please note that this table only display AEs occurring >=5% subjects during Maintenance phase	WK48
3.39.	Safety	Shell TS15	Summary of Adverse Events by System Organ Class and Baseline ART Third Agent Class – Maintenance Phase		WK48
Injection Site Reaction Adverse Events					
3.40.	Safety	Shell TS2.2	Summary of Injection Site Reaction Adverse Events (Event-Level Summary) –Maintenance Phase	(for Q4W arm only)	HL, WK48
3.41.	Safety	Shell TS2.2	Summary of Injection Site Reaction Adverse Events (Event-Level Summary) –Maintenance + Extension Phase	(for Q4W arm only)	WK96, EOS
3.42.	ESP	Shell TS2.2	Summary of Injection Site Reaction Adverse Events (Event-Level Summary) –Extension Phase	(for Current ART arm only)	WK96, EOS

Safety Tables (Displays will be for both treatment arms, unless specified)					

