13.13.8. Safety Figures

Safety : Figures					
No.	Population	IDSL / TST ID / Example Shell	Title	Programming Notes	Deliverable [Priority]
Adverse Events					
3.1.	Safety	AE10	Plot of Common Adverse Events and Relative Risk-Q4W vs Current ART at Maintenance Phase	CS CORE	HL, WK 48
3.2.	Safety	LIVER9	Scatter Plot of Maximum vs. Baseline for ALT (Maintenance Phase)	CS CORE	HL, WK 48
3.3.	Safety	LIVER9	Scatter Plot of Maximum ALT vs. Maximum Total Bilirubin (Maintenance Phase)	CS CORE	HL, WK 48
3.4.	Safety	Shell FS2/	Matrix Plot of Maximum Liver Chemistries at Maintenance Phase	CS CORE	HL, WK 48
3.5.	Safety	Shell FS3/	Plot of Onset, Duration, and Severity of Overall and Common Maintenance Phase Injection Site Reaction AEs by Maximum Grade: CAB/RPV		WK 48
3.6.	Safety	Shell FS3/	Plot of Onset, Duration, and Severity of Overall and Common Maintenance Phase Injection Site Reaction AEs by Maximum Grade: CAB		WK 48
3.7.	Safety	Shell FS3/	Plot of Onset, Duration, and Severity of Overall and Common Maintenance Phase Injection Site Reaction AEs by Maximum Grade: RPV		WK 48
3.8.	Safety	Shell FS4/	Plot of Incidence of Maintenance Phase Injection Site Reaction Adverse Events-Overall and Common – CAB/RPV		WK 48
3.9.	Safety	Shell FS4/	Plot of Incidence of Maintenance Phase Injection Site Reaction Adverse Events-Overall and Common – CAB		WK 48
3.10.	Safety	Shell FS4/	Plot of Incidence of Maintenance Phase Injection Site Reaction Adverse Events-Overall and Common – RPV		WK 48
3.11.	Safety	Shell FS4/	Plot of Incidence of Grade 3-5 Maintenance Phase Injection Site Reaction Adverse Events - Overall and Common - CAB/RPV		WK 48

Safety : Figures					
No.	Population	IDSL / TST ID / Example Shell	Title	Programming Notes	Deliverable [Priority]
3.12.	Safety	Shell FS4/	Plot of Incidence of Grade 3-5 Maintenance Phase Injection Site Reaction Adverse Events - Overall and Common - CAB		WK 48
3.13.	Safety	Shell FS4/	Plot of Incidence of Grade 3-5 Maintenance Phase Injection Site Reaction Adverse Events - Overall and Common - RPV		WK 48
3.14.	Safety	Shell FS1	Bar Chart of Fasting LIPID NCEP Categories for Triglycerides, Total Cholesterol, and LDL at Week 48 vs. Baseline	Example: arenv/arprod/gsk3365791/mid_dori_ph3/week48/outputs/figure 3.062	WK 48
3.15.	Safety	Shell FS1	Bar Chart of Fasting LIPID NCEP Categories for HDL at Week 48 vs. Baseline		WK 48

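### Injection-site reactions still open at the data cut get no duration, so statistics on reaction duration rest on resolved reactions only and lean short

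*SAP*

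**What the plan says.** SAP 13.4.2.1 (Table 21) defines AE duration as "AE Resolution Date – AE Onset Date + 1", which needs a resolution date.

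SAP 13.7.2.1 gives the rules for incomplete AE dates. A stop date lacking only its day is filled in: "Last day of the month will be used, unless this is after the stop date of study treatment". For a wholly absent date, "Completely missing start or end dates will remain missing, with no imputation applied", and the section adds "Consequently, time to onset and duration of such events will be missing".

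ISR duration is nevertheless a planned output. Section 8.4, Table 5 note 20, describes the event-level summary: "Percentages based on total number of ISR events within each treatment group including distribution of grade, duration, and event characteristics". Table 3.40, "Summary of Injection Site Reaction Adverse Events (Event-Level Summary) –Maintenance Phase", is a headline and Week 48 deliverable. Tables 3.47 (CAB) and 3.51 (RPV) use the same shell at Week 48, and Tables 3.41 and 3.42 do so at Week 96 and end of study. Figures 3.5 to 3.7 also show duration; the first is "Plot of Onset, Duration, and Severity of Overall and Common Maintenance Phase Injection Site Reaction AEs by Maximum Grade: CAB/RPV".

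**The concern.** A reaction that has not resolved when the database is cut has no end date. Under the two rules together its duration is missing, and any mean, median or percentile is taken over resolved reactions only. Whether a reaction is left out depends on how long it lasts: of two reactions starting on the same day, the longer one is more likely to be open at the cut. The omission is therefore informative, and it can only shorten the reported durations.

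Percentages are affected differently. Note 20 bases them on all ISR events, so open reactions stay in the denominator but cannot be placed in a duration category. Long-duration categories then read too low, unless the table shell (not shown) has a row for ongoing or missing events.

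At stake is how persistent injection-site reactions look in the safety section of the report. No efficacy conclusion depends on it.

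**Working it through.** **Is there a rule elsewhere that rescues open reactions?** The partial-date rule in 13.7.2.1 covers only a missing day of the month. Nothing in 8.4, 13.4.2.1, 13.6.3 or 13.7 gives an ongoing AE a provisional end date, a censored value or its own category. The SAP does handle the same situation in other places: the disposition tables (6.1, note 5) have a category for subjects neither completed nor withdrawn, and Appendix 15 censors time-to-event data at the cut-off. ISR duration has neither.

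**Size.** The SAP states no figure for ISR duration or for the share of ISRs open at the cut, so there is nothing to reproduce. The rule was simulated instead.

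Inputs from the SAP: injections every 4 weeks from Week 4b (13.6.4), taken as 12 visits on Days 29 to 337; analysis only after all subjects have completed Week 48 (3.2), so the cut falls at the last subject's Week 48.

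Assumptions not in the SAP: uniform accrual over A = 180 or 365 days; each reaction equally likely to follow any of the 12 visits; lognormal duration with median m and log-SD s; no dropout.

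Formulas:
- Study day at the cut for a subject entering at time e: 337 + (A − e).
- A reaction is open if injection day + duration exceeds that day.
- True mean = m × exp(s²/2), for example 28 × exp(0.5) = 46.2 days.
- Change = resolved-only value ÷ true value − 1.

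Results, 3,000,000 reactions per setting:

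| log-SD | Median (d) | True mean (d) | Accrual (d) | Open at cut | Resolved-only mean (d) | Change in mean | Change in median |
|---|---|---|---|---|---|---|---|
| 1.0 | 3 | 4.9 | 180 | 0.2% | 4.9 | −0.6% | −0.2% |
| 1.0 | 3 | 4.9 | 365 | 0.1% | 4.9 | −0.3% | −0.1% |
| 1.0 | 14 | 23.1 | 180 | 1.7% | 21.7 | −5.9% | −1.8% |
| 1.0 | 14 | 23.1 | 365 | 0.9% | 22.3 | −3.5% | −0.9% |
| 1.0 | 28 | 46.2 | 180 | 4.9% | 39.5 | −14% | −5.2% |
| 1.0 | 28 | 46.2 | 365 | 2.6% | 41.8 | −9% | −2.9% |
| 1.5 | 7 | 21.6 | 180 | 2.2% | 16.9 | −22% | −3.8% |
| 1.5 | 7 | 21.6 | 365 | 1.3% | 18.0 | −16% | −2.2% |
| 1.5 | 28 | 86.2 | 180 | 10.8% | 43.3 | −50% | −18% |
| 1.5 | 28 | 86.2 | 365 | 7.3% | 49.5 | −43% | −12% |

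Repeat runs moved the heavy-tailed means by one or two points, hence the ranges of 15–22% and 41–50% in the summary.

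**Percentages over all ISRs.** In a run with 285 subjects (half of 570), an assumed 30% ISR risk per injection, log-SD 1, median 30 days and 180-day accrual, 50.0% of reactions truly lasted more than 30 days. Among resolved reactions the share was 47.5%. Over all reactions it was 47.5% × (1 − 0.054) = 44.9%, because the 5.4% still open could not be placed. The 30-day threshold is only for illustration; the SAP states no duration categories.

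**Does censoring repair it?** With 180-day accrual, log-SD 1.5 and a nominal median of 30 days, the true median was 31 days, the resolved-only median 25 and the Kaplan-Meier median 31. With a nominal median of 7 days all three were 7.

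**The case against.** Section 13.7.2.1 does not mention ongoing events or a data cut; applying it to them is an inference. It is a sound one, because the duration formula cannot be evaluated without a resolution date, but the table shell could still contain an ongoing row. What is certain is therefore limited to statistics on the duration value itself.

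A reader might infer that the longest reactions are removed. The documents do not support that. The rule removes reactions open at the cut, which are long on average but include recent ordinary ones; a long reaction that began early and resolved stays in. In the settings tabulated, about 17% to 58% of the open reactions lay outside the longest tenth.

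A reader might also expect a larger effect by cutting every participant soon after the Week 48 injection. At Day 350 for all, with log-SD 1 and a 28-day median, 14% of reactions would be open and the mean would read 36 instead of 46 days (−22%). Section 3.2 contradicts that cut: the analysis waits for the last subject, so earlier entrants have longer follow-up. Table 16 assigns AEs to phase by start date, so a Maintenance Phase reaction that resolves in the Extension Phase before the cut keeps its duration.

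Finally, ISR duration might be taken for a main tolerability result. It is not a listed endpoint in Section 2.2; it is one item in a table note, with no test attached. These objections limit the size and importance of the point. They do not supply the missing rule.

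**Conclusion.** The point holds as a minor one. As written, duration statistics for ISRs rest on resolved reactions and are biased downward or, at best, unaffected. The direction follows from the rule; the size does not. For short reactions the effect is negligible. It becomes visible if reactions typically last weeks, and material if the distribution has a heavy tail. Induration and nodules are among the SAP's common ISRs (8.4), but nothing in the document says how long they last, so it cannot be said that they in particular would be lost. All figures depend on the assumed accrual period and duration distribution. The simulated cut is the Week 48 one; Tables 3.41 and 3.42 follow the same rule at a later cut that was not modelled. The primary and key secondary analyses are untouched.

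**What to change.** In 13.7.2.1 and in Table 5 note 20, state that ISRs ongoing at the cut are kept. Report their number and percentage in Tables 3.40 to 3.42, 3.47 and 3.51. Summarise duration by the Kaplan-Meier median and quartiles at event level, with ongoing reactions censored at the earlier of data cut and last contact. Label this descriptive, and note that one participant can contribute several reactions, so the events are not independent. If only one change is made, the count of ongoing reactions is the one to add, since it tells the reader how complete the duration summary is.

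The cost is a sentence or two in the SAP, a row in each table and slightly less simple summary statistics. No new data are needed.
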